## 2.5 Sample Size Consideration

Approximately 70 subjects will be screened to have at least 45 subjects who complete the study.

The primary analysis is based on the score of cervical mucus as a quantitative variable because it is expected to be the most powerful analysis based on the consistent mechanism of action of norgestrel on cervical mucus. However the justification of the sample size will not be based on the primary analysis as there is no basis provided by published data on this parameter, such as order of magnitude of the variance covariance matrix of the change from time point of reference. This is the reason why the sample size calculation will be based on proportions of women with no loss of protection.

A total sample size of 45 subjects who complete the study should allow to detect a loss of protection that would demonstrate a pertinent effect on a substantial proportion of the population. Indeed if the difference between a cycle (or day) with a perfect use and a cycle (or day) with an infringement in the schedule is 14 % in the expected proportions of women with a loss of protection at any time and if the proportion of discordances between the 2 situations is 17% then the exact power is equal to 79.1%. If the expected difference in proportions is 15% with a rate of discordance of 18% then the exact power is 82.4% for an unconditional test. The expected difference in proportions need, therefore, to reach 14-15 % to get a sufficient power for detecting a significant difference. This difference in proportions is a substantial difference knowing that most of change in status are in the same direction i.e. from protection to loss of protection.

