## 3.0 STATISTICAL METHODS

### 3.1 Statistical Handling Policy and Analysis Conventions

This section details general policies to be used for the statistical analyses. Departures from these general policies may be given in the specific detailed sections of this SAP. When this situation occurs, the rules set forth in the specific section take precedence over the general policies. The following policies will be applied to all data presentations and analyses.

- All statistical tests will use a significance level of  $\alpha = 0.05$ . Two-tailed tests will be performed for all analyses that use statistical testing.
- All p-values will be rounded to 3 decimal places. All p-values that round to 0.000 will be presented as '<0.001' and p-values that round to 1.000 will be presented as '>0.999'. Any

p-value  $\leq 0.05$  will be considered statistically significant and will be marked with one asterisk (e.g., 0.025\*).

- Summary statistics will consist of the number and percentage of responses in each category for discrete variables, and the mean, median, standard deviation (SD), minimum, and maximum for continuous variables.
- All mean values will be formatted to one more decimal place than the measured value. Standard deviation values will be formatted to two more decimal places than the measured value. Median values will be formatted to same decimal place as the measured values when that is possible without losing accuracy; otherwise, they will be formatted to one more decimal place than the measured values.
- All percentages will be rounded to one decimal place. The number and percentage of responses will be presented in the form XX (XX.X), where the percentage is in the parentheses. The denominator for percentage calculations will be the number of non-missing observations.
- All listings will be sorted for presentation in order of site number, subject number, and date of procedure or event.
- All analysis and summary tables will have the population sample size (n and % (% will not be shown in the column header if the table also presents means)) for each treatment group in the column heading.
- Calculating change from baseline to a visit will be done as follows: Change = Visit – Baseline.
- Baseline is defined as the last data point before the day of infringement (i.e. V2R-1 or V3R-1).
- Version 9.4 of SAS® or higher will be the statistical software package used to produce all summaries, listings, statistical analyses, and graphs.

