Comparison between the missed pill and the delayed pill can easily be performed and tested through a stratified McNemar test (stratification on the site, CMH option in SAS). The SAS glimmix procedure for repeated measures was not retained for decision making test because convergence issues in fitting the model are too frequent. The first null hypothesis is  $H_0$ : Proportion of protected women at baseline (R-1) is equal to the proportion of protected women after schedule infringement and more specifically at Day R (27 hours and 30 hours post treatment). The second null hypothesis (which is only performed for the missed pill arm) is the equality of proportions at baseline (R-1) and at Day R+1 (48 hours post treatment).

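### The power quoted for 45 completers (79.1% and 82.4%) matches a one-sided 5% test; under the SAP's two-tailed 0.05 rule it is 69.5% and 73.6%

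*SAP*

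**What the plan says.** SAP section 2.5 explains that the sample size does not rest on the primary mixed model, because no published variance data exist for it. It rests instead on the proportion of women who lose protection, compared within subject between perfect use and an infringement. The claim is that "A total sample size of 45 subjects who complete the study should allow to detect a loss of protection". Two scenarios support it:

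- Scenario 1 assumes a 14-point gap in the share of women losing protection: "if the proportion of discordances between the 2 situations is 17% then the exact power is equal to 79.1" percent.
- Scenario 2 assumes a slightly larger gap, which "is 15% with a rate of discordance of 18% then the exact power is 82.4% for an unconditional test".

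From these it is concluded that a difference of 14-15% is what sufficient power requires. No alpha is given there, and it is not said whether the test is one- or two-sided.

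Section 3.1 supplies both for the whole plan. Alpha is 0.05, "Two-tailed tests will be performed for all analyses that use statistical testing", and a p-value of 0.05 or less counts as significant. Specific sections may override these conventions. The sections that prescribe the McNemar tests (the subordinate primary objective in 3.7.1, and 3.7.2.1 and 3.7.2.2) specify a site-stratified McNemar test and do not override them. Section 3.7.1 writes its null hypotheses as equality of proportions.

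**The concern.** A power figure is valid only for the test and significance rule for which it was computed. Section 2.5 leaves the rule unstated, so a reader will apply that of section 3.1. If the figures came from a more lenient rule, 45 completers do not give the stated power in the analysis as planned.

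The comparison asks whether a delayed or missed pill causes loss of cervical mucus protection, so a non-significant result may be read as reassuring. How far it reassures depends on the power. A reader told that power is about 80% would give such a result more weight than it deserves.

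**Working it through.** **Inputs**

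- n = 45 completers (section 2.5).
- Scenario 1: difference d = 0.14, discordance q = 0.17, stated power 79.1% (section 2.5).
- Scenario 2: d = 0.15, q = 0.18, stated power 82.4% (section 2.5).
- Test form: exact power of an unconditional test (section 2.5).
- Alpha 0.05, two-tailed (section 3.1).

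**Discordant-cell probabilities.** Let p10 be the probability of moving from protected to unprotected, and p01 the reverse:

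p10 = (q + d)/2 and p01 = (q − d)/2

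- Scenario 1: p10 = (0.17 + 0.14)/2 = 0.155; p01 = (0.17 − 0.14)/2 = 0.015.
- Scenario 2: p10 = (0.18 + 0.15)/2 = 0.165; p01 = (0.18 − 0.15)/2 = 0.015.

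**Test.** With b and c discordant pairs in the two directions, the statistic is z = (b − c)/√(b + c). The critical value is the smallest attainable one for which the rejection probability under p10 = p01, maximised over the unknown discordance rate, does not exceed alpha.

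**Power.** Sum over all (b, c) in the rejection region:

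n! / [b! c! (n − b − c)!] × p10^b × p01^c × (1 − q)^(n − b − c)

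**Reproducing the stated figures, then applying section 3.1 (n = 45)**

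| Rule | Critical value | 14% / 17% | 15% / 18% |
|---|---|---|---|
| Stated in section 2.5 | not given | 79.1% | 82.4% |
| One-sided 0.05 | 1.698 | 79.10% | 82.43% |
| Two-sided 0.05 | 2.000 | 69.46% | 73.61% |

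The one-sided 5% test matches both printed figures to the decimal. A two-sided test at 0.10 has the same critical value and gives the same powers.

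**Could another two-sided 0.05 form of the test give the stated figures?**

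| Two-sided 0.05 variant | 14% / 17% | 15% / 18% |
|---|---|---|
| Uncorrected asymptotic McNemar, exact power | 69.5% | 73.6% |
| Mid-p | 65.3% | 70.4% |
| Exact conditional | 52.1% | 58.0% |
| Continuity-corrected | 52.1% | 58.0% |
| Normal approximations (two formulas) | 63.2%, 68.0% | 67.0%, 73.1% |

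None exceeds 69.5% and 73.6%.

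**Size of the overstatement**

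- Scenario 1: 79.10 − 69.46 = 9.64 points; type II error 100 − 69.46 = 30.5%, against 20.9% as stated.
- Scenario 2: 82.43 − 73.61 = 8.82 points; type II error 100 − 73.61 = 26.4%, against 17.6% as stated.

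**Difference needed with 45 completers.** In both scenarios discordance exceeds the difference by 3 points, so p01 stays at 0.015. Keeping that gap, two-sided 0.05 power is 79.1% at 16.5% / 19.5% and 80.7% at 17% / 20%.

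**The case against.** The arithmetic is not in dispute, but several points can be made about its reading.

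- *One-sidedness is inferred.* Section 2.5 does not state it, and a two-sided 10% test fits equally well. This stands as a point of wording. The finding does not depend on which of the two was used, since neither agrees with section 3.1.
- *A directional calculation may have been deliberate.* Section 2.5 remarks that most changes of status go one way, and section 3.7.1 hypothesises a negative impact. Even so, planning on one rule and testing on another needs to be stated, and no section adopts a one-sided test.
- *The consequence is limited.* The study is exploratory, the primary analysis is a mixed model on the quantitative score, and no 80% target is set. All of this is true. The error biases no estimate or p-value and concerns only the binary comparisons. But section 2.5 chose those comparisons as the basis of the sample size, so the erroneous figures are the whole of its numerical support.
- *The recomputed powers ignore site stratification.* Correct: 69.5% and 73.6% are for the unstratified test and should be labelled so. Section 2.5 mentions no stratification in its own calculation either.
- *The exact conditional test is not what the SAP calls for.* Also correct. The 52.1% and 58.0% figures show only that this form does not rescue the stated power; they are no part of the size of the error.

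**Conclusion.** The concern holds. With 45 completers and the SAP's own scenarios, an unstratified exact unconditional McNemar test at two-sided 0.05 has power 69.5% and 73.6%, not 79.1% and 82.4%. The uncorrected asymptotic McNemar test gives the same values. That the originals came from a one-sided 5% calculation (or its two-sided 10% equivalent) is an inference, but it fits both figures exactly.

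The statement that a 14-15% difference gives sufficient power needs to change with them. At the two-sided rule, the SAP's lower power figure of 79.1% is reached at about 16.5%, and 80% is passed at about 17%. Both rest on the assumption that the reverse-direction probability stays at 1.5%. For scale only, the original scenarios would need about 58 completers (14% / 17%) or 54 (15% / 18%) for at least 80% power on the same test.

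**What to change.** Restate section 2.5 for the test that section 3.1 requires:

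- Give alpha as two-sided 0.05 and name the test form (unconditional or uncorrected asymptotic McNemar, unstratified for the power calculation), so that planning and analysis can be compared.
- Replace the two powers with 69.5% (difference 14%, discordance 17%) and 73.6% (15%, 18%).
- Replace the closing statement on 14-15% with the difference that 45 completers can detect: about 17%, with 20% discordance, for 80.7% power.

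The cost is wording in one section and a less favourable power statement. The number of subjects, the endpoints and the analyses do not change. Keeping the old figures and declaring the tests one-sided would be a change to the analysis rule, not a correction of the power statement.

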## 3.0 STATISTICAL METHODS

### 3.1 Statistical Handling Policy and Analysis Conventions

This section details general policies to be used for the statistical analyses. Departures from these general policies may be given in the specific detailed sections of this SAP. When this situation occurs, the rules set forth in the specific section take precedence over the general policies. The following policies will be applied to all data presentations and analyses.

- All statistical tests will use a significance level of  $\alpha = 0.05$ . Two-tailed tests will be performed for all analyses that use statistical testing.
- All p-values will be rounded to 3 decimal places. All p-values that round to 0.000 will be presented as '<0.001' and p-values that round to 1.000 will be presented as '>0.999'. Any

p-value  $\leq 0.05$  will be considered statistically significant and will be marked with one asterisk (e.g., 0.025\*).

- Summary statistics will consist of the number and percentage of responses in each category for discrete variables, and the mean, median, standard deviation (SD), minimum, and maximum for continuous variables.
- All mean values will be formatted to one more decimal place than the measured value. Standard deviation values will be formatted to two more decimal places than the measured value. Median values will be formatted to same decimal place as the measured values when that is possible without losing accuracy; otherwise, they will be formatted to one more decimal place than the measured values.
- All percentages will be rounded to one decimal place. The number and percentage of responses will be presented in the form XX (XX.X), where the percentage is in the parentheses. The denominator for percentage calculations will be the number of non-missing observations.
- All listings will be sorted for presentation in order of site number, subject number, and date of procedure or event.
- All analysis and summary tables will have the population sample size (n and % (% will not be shown in the column header if the table also presents means)) for each treatment group in the column heading.
- Calculating change from baseline to a visit will be done as follows: Change = Visit – Baseline.
- Baseline is defined as the last data point before the day of infringement (i.e. V2R-1 or V3R-1).
- Version 9.4 of SAS® or higher will be the statistical software package used to produce all summaries, listings, statistical analyses, and graphs.

### **3.2 Subject Disposition**

Subject disposition will be summarized for the All Enrolled population (see Section 3.4 for Analysis Population definitions). The following data will be presented:

- The number and percentage of subjects who completed or discontinued prematurely from the study by each treatment phase (reported perfect use, delayed pill intake and missed pill) will be presented. The number and percentage of subjects who discontinued for each reason will also be summarized.
- A listing of subjects that discontinued prematurely from the study. The listing will include site number, subject number, age, number of days on drug, and reason for discontinuation. The number of days on drug will be calculated using the reported dosing days based on diary data.
- The number and percentage of subjects at each scheduled visit for all subjects.

The End of Trial (DS) CRF will be used to determine who discontinued prematurely from the study.

### 3.3 Protocol Deviations

The number and percentage of subjects with each protocol violation and the total will be tabulated for all subjects for the Intent-to-Treat population.

### 3.4 Analysis Populations

All Enrolled – This population includes all successfully screened subjects enrolled in the study. AE will be primarily used for baseline and demographics tables including disposition.

Safety (SAF) – This population consists of all subjects who took at least one dose of study medication.

The Safety (SAF) set will be used for safety purposes including adverse events, intermenstrual bleedings and labs data, but also to describe the population and to summarize and describe the level of compliance based on daily intake.

Intent-to-Treat (ITT) – This population consists of all subjects who were randomized. ITT will be the primary population used for sensitivity analyses.

The ITT population will be used in the primary sensitivity analysis for assessing the effect of delayed or missed pill on cervical mucus scores and on secondary pharmacodynamic analyses.

Full Analysis Set – This population consists of all **evaluable subjects**. These are subjects who have complete (including mitigated) data on cervical mucus and ovarian activity for the adjudication committee to assess evaluability of a cycle. They will be classified into 3 analysis populations depending on the question of interest. There are 3 full analysis sets defined: Cervical Mucus, Ovarian Activity and Conception Protection. Full analysis set requires at least one evaluable treatment cycle.

- Full Analysis Set – Cervical Mucus (FASM) – This population is composed of all randomized and treated subjects with **cervical mucus** information (mucus score) at the second or third treatment periods for the questions related to mucus on the effect of unperfect use (delayed and missed intake) of norgestrel.
- Full Analysis Set – Ovarian Activity (FASO) – This population consists of all randomized and treated subjects with ovarian activity information (OAS: ovarian activity score) at the second or third treatment periods for questions related to **ovarian activity**.
- Full Analysis Set – Conception Protection (FASC) – This population consists of all randomized and treated subjects with information on mucus and ovarian activity for questions related to **overall conception protection**.

Cycles with a very early ovulation (within 10 days before the DMP period) at period 2 or 3 may be removed from the set of evaluable cycles in a sensitivity analysis or included as failure

depending upon the question of interest because the effect of intake infringement cannot be assessed in these cycles. The assessment of evaluable cycles, the exclusion of cycles from a given analysis and the exclusion of a subject from the FASM/FASO/FASC will be decided in a blinded manner by an independent adjudication committee.

The FASM, FASO and FASC (or evaluable populations) will be used in the primary analysis for assessing the effect of delayed or missed pill on cervical mucus scores and on secondary pharmacodynamic analyses.

Per-protocol (PP) – This population consists of all subjects from the FASM/FASO/FASC without major protocol violation/deviation and with complete cervical mucus and ovarian activity data for all the three treatment periods. Relevant protocol violation/deviation will be defined during the data review. This will include pill intake compliance issues and early ovulation.

The PP population will be used for assessing the efficacy and PK results without missing data and possibly biased data due to protocol violations/deviations. This will be the "cleanest" results for assessing the effect of infringement and the PD effect at the expense of completeness of the set of randomized women and representativeness of the treated population.

The number of subjects in each population will be summarized for all subjects.

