### 3.7.2.2 Ovarian activity in each type of treatment period

The aim of this secondary objective is to describe the distribution of the ovarian status among the subjects, during reported perfect use, during a treatment period with a delayed pill intake of 6 hours and during a treatment period with a missed pill of norgestrel 75 mcg. The adjudication committee will evaluate whether cycles should be excluded from analyses (including period 1 cycles if low compliance of taking study drug). The details for the review process will be defined in a separate document prepared for the adjudication process. The FASO population will be used for the analysis and a sensitivity analysis will be done using ITT and PP.

The time frames are:

- reported perfect use period: all the visits of the period 1
- delayed pill intake period: all the visits of the period 2 for Arm A and all the visits of period 3 for Arm B
- missed pill period: all the visits of the period 2 for Arm B and all the visits of period 3 for Arm A

The assessment criterion is the OS as defined in Appendix 5.4.

The OS are ranked depending on the risk of conception:  $OS_{nlp} > OS_{alp} > OS_a > OS_q$ . The OS classification will be determined by the adjudication committee.

For each treatment period the most risky OS will be considered.

The endpoints are:

- The percentage of subjects with  $OS_q$ ,  $OS_a$ ,  $OS_a/OS_{alp}$  and  $OS_{nlp}$  in reported perfect use period
- The percentage of subjects with  $OS_q$ ,  $OS_a$ ,  $OS_a/OS_{alp}$  and  $OS_{nlp}$  in delayed pill intake periods
- The percentage of subjects with  $OS_q$ ,  $OS_a$ ,  $OS_a/OS_{alp}$  and  $OS_{nlp}$  in missed pill periods
- The percentage of subjects with  $OS_{nlp}$  in all periods

A stratified McNemar test (stratification on the site, CMH option in SAS) will be used to compare the distribution of ovarian activity classification in the perfect use period to the delayed and missed pill periods (pairwise vs perfect use). The worst (meaning most risk of ovulation) ovarian activity category in the period will be used for the analyses.

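### The only written definition of early ovulation, a per-protocol exclusion, covers periods 2 and 3 alone; on that reading the PP ovarian and conception tables are selected on their own outcome

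*SAP*

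**What the plan says.** Section 3.4 defines the PP set by subject: "This population consists of all subjects from the FASM/FASO/FASC without major protocol violation/deviation". It also requires that each woman's mucus and ovarian data be complete in every period. On the deviations themselves it states: "Relevant protocol violation/deviation will be defined during the data review". It then fixes two items in advance: "This will include pill intake compliance issues and early ovulation". That sentence names no period.

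The only description of early ovulation is in the same section, under the full analysis sets: "Cycles with a very early ovulation (within 10 days before the DMP period) at period 2 or 3 may be removed". The removal, which concerns the cycles treated as evaluable, is optional. It belongs to a sensitivity analysis, and the alternative offered is to count such cycles as failures, depending on the question. The stated reason is that the effect of the infringement cannot be assessed in them. An independent committee decides, blinded.

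Section 3.7.2.2 takes the riskiest ovarian status in each period and compares each infringement period with perfect use by a stratified McNemar test. The comparator is "reported perfect use period: all the visits of the period 1". The only reason given there for excluding a period 1 cycle is low compliance. On populations: "The FASO population will be used for the analysis and a sensitivity analysis will be done using ITT and PP". Section 3.7.2.3 does the same with FASC, combining ovarian status with mucus score. Section 5.5 lists the PP versions as Tables 14.2.14 and 14.2.19.

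**The concern.** Ovulation on treatment is a pharmacodynamic result, not a departure from study conduct. A set that drops women because they ovulated is selected on the outcome it then tabulates. If the rule looks only at periods 2 and 3, the selection is also one-sided: an ovulation on a given cycle day can count against perfect use but not against a delayed or missed pill.

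The rationale in Section 3.4 suits the mucus change around the infringement, where an ovulation beforehand does spoil the measurement. It does not carry over to a comparison of whole periods unless the matching days of period 1 are set aside too.

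At stake is how the PP tables are read. The bias makes infringement look no worse than perfect use, or even better. Section 3.4 presents PP as the least contaminated answer on the effect of infringement, so a disagreement with FASO could be settled in favour of the biased table.

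**Working it through.** **Window.** Section 5.1 puts the period 2 DMP days at D41 to D43 (±3). The 10 days before are nominally D31 to D40. Period 2 starts on D29, so these are days 3 to 12 of a 28-day period. Period 1 has the same cycle days but no DMP days to anchor a window.

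**Inputs.** The SAP states no ovulation rate, no share of early ovulations and no expected PP size, so there is no figure to reproduce. Assumed: infringement has no effect; each period has ovulation probability π; a share f = 10/28 = 0.357 of ovulations falls in the window (an even spread over the period); a woman leaves PP if she ovulates in the window in period 2 or 3.

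**No within-woman correlation.** Period 1 rate in PP = π. Period 2 or 3 rate = π(1−f)/(1−πf). Share of women kept = (1−πf)².

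At π = 0.30: 0.30 × 0.643 / (1 − 0.107) = 0.193/0.893 = 21.6%, against 30.0% in period 1. Kept: 0.893² = 0.797, about 36 of the 45 planned completers.

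**Correlation 0.3 between a woman's periods.** Let her own probability q follow a beta distribution with mean π and variance 0.3π(1−π).

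- Share kept: D = E[(1−fq)²]
- Period 1 rate: E[q(1−fq)²]/D
- Period 2 or 3 rate: (1−f)E[q(1−fq)]/D

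At π = 0.30: E[q²] = 0.09 + 0.3 × 0.21 = 0.153, and E[q³] = 0.153 × 2.7/4.333 = 0.0953.

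- D = 1 − 0.2143 + 0.0195 = 0.805
- Period 1: (0.3 − 0.1093 + 0.0122)/0.805 = 25.2%
- Period 2 or 3: 0.643 × (0.3 − 0.0546)/0.805 = 19.6%

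| Assumed π | Correlation 0: period 1 v 2/3 (gap) | Correlation 0.3: period 1 v 2/3 (gap) | Women lost at correlation 0 |
|---|---|---|---|
| 20% | 20.0 v 13.8 (6.2) | 16.5 v 12.5 (4.0) | 13.8% |
| 30% | 30.0 v 21.6 (8.4) | 25.2 v 19.6 (5.6) | 20.3% |
| 40% | 40.0 v 30.0 (10.0) | 34.2 v 27.4 (6.8) | 26.5% |

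**Other settings.** A simulation of 400,000 women per setting placed the correlation on a latent normal scale, where 0.3 means a weaker link between the yes/no outcomes. At 0.3 it gave gaps of 5.0, 6.8 and 7.8 points for π of 20, 30 and 40%. At π = 30% the gap fell to 4.7 points at 0.6 and 2.3 at 0.9. Over π from 10 to 50%, f from 20 to 50% and correlation from 0 to 0.9, it ran from about 0.6 to 17 points and never changed sign.

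**Symmetric rules.** At π = 30% and no correlation, applying the window to all three periods gives 21.6% v 21.6%. Applying no ovulation rule gives 30% v 30%. The false gap disappears either way.

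**The case against.** The strongest reply is that the SAP does not say what a reader might infer, namely that PP definitely keeps the period 1 ovulations and so shows fewer in infringement periods by construction. The PP sentence names no period and leaves the details to data review. The definition for periods 2 and 3 sits in a different rule, uses the term *very early*, and is not cross-referenced. This stands. The bias follows from the only definition available, and data review could still extend the rule to period 1. But nothing written does so, and an exclusion based on the outcome should not be left until the data are in view.

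Second, PP drops whole women, so it does not set an intact period 1 against purged later periods. This also stands: at correlation 0.3, period 1 itself falls from 30% to 25.2%. The gap narrows but does not close.

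Third, Section 3.4 also allows early-ovulation cycles to be counted as failures, which is the natural choice when ovulation is the outcome. That option belongs to the full analysis sets, where removal is optional. It means no fixed defect is shown for FASO or FASC. It does not change the PP exclusion.

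Fourth, the stakes are limited. The study is exploratory, these outcomes are secondary, and PP appears beside FASO or FASC and ITT, so a divergence would be visible. The conception comparison has no test (Section 2.4.2), and a woman who ovulates with a mucus score of 4 or less still counts as protected, which dilutes the effect there. All of this stands and limits the consequence.

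Blinded adjudication is no answer: it does not make a one-sided rule symmetric.

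**Conclusion.** The point holds as a conditional one. Early ovulation is a named PP exclusion, it overlaps the outcome of Sections 3.7.2.2 and 3.7.2.3, and the only written definition covers periods 2 and 3. On that reading, Tables 14.2.14 and 14.2.19 are biased in expectation towards fewer ovulations under infringement. A true effect of infringement could outweigh the bias.

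The size rests wholly on assumed inputs. In women, a gap of 8.4 points among about 36 retained is about three; at correlation 0.3, 5.6 points among about 36 (0.805 × 45) is about two. The lower figures deserve more weight, because the same women supply all three periods. No size is given for conception protection.

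A reader might go further and conclude that the main ovarian and conception results are biased. The documents do not support that: FASO and FASC are the main sets, ITT is also run, and these are affected only if the optional cycle removal is used. The matter should be settled before data review, but it does not threaten the primary analysis.

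**What to change.** In Section 3.4, before data review, take one of two courses for Tables 14.2.14 and 14.2.19:

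1. Define PP by intake and procedural deviations only, with no exclusion based on ovulation, and make no ovulation-based cycle removal in FASO or FASC sensitivity analyses.
2. If ovulations before the infringement are to be set aside, apply the same cycle-day window to periods 1, 2 and 3.

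State the chosen definition of early ovulation in the PP paragraph itself. The early-ovulation exclusion may stay for the mucus-change analysis.

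The cost is SAP wording and one extra population flag. Course 1 also keeps some ovulations that preceded the infringement and cannot reflect it, which dilutes the contrast.
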